9.2.1. Stopping Criteria

Potential discontinuation of study drug for abnormal liver function tests should be considered if the study participant meets one or more of the following liver chemistry threshold stopping criteria:

- ALT or AST \geq 4x ULN;
- ALT or AST $\geq 3x$ ULN and total bilirubin $\geq 2x$ ULN;
- ALT or AST \geq 3x ULN if associated with the appearance or worsening of fatigue, nausea, vomiting, right upper quadrant pain or tenderness, fever, rash and/or eosinophilia;

or

- ALP elevations, if deemed of liver origin and drug-related as follows:
 - \circ ALP > 3x ULN;
 - \circ ALP > 2.5x ULN and total bilirubin > 2x ULN; or
 - ALP > 2.5x ULN if associated with the appearance or worsening of fatigue, nausea, vomiting, right upper quadrant pain or tenderness, fever, rash and/or eosinophilia,

where ULN = Upper Limit of Normal.

Study drug should be discontinued if a participant: (1) positively affirms suicidal ideation in response to questions number 4 or 5 in the suicidal ideation section of the C-SSRS, or (2) reports any suicidal behavior or non-suicidal self-injurious behavior since their last visit in response to the C-SSRS Suicidal Behavior questions.

Bodyweight loss (compared to weight at Baseline Visit [Study Day 1]) of \geq 2 kg resulting in a BMI < 18.5 is an additional stopping criterion.

Individual results of stopping criteria will be listed and summarized by presenting the number and percentage of participants who meet at least one post-dose stopping criteria.

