3.2.1. Safety Endpoints

The safety endpoints of this study include the following:

• Incidence of adverse events (AEs) including treatment-emergent, serious, related to study

Version 1.0 | 28-Feb-2025 Page 16 of 56

drug, and leading to withdrawal along with AEs by severity and relationship to study drug

- Mean change in clinical laboratory values from baseline to Weeks 4, 16, 28, 40, 52, 64 and 76. Shifts in the normality of clinical laboratory values from baseline to Weeks 4, 16, 28, 40, 52, 64 and 76.
- Mean change in vital signs (blood pressure [supine], temperature, pulse rate) from baseline to Weeks 4, 16, 28, 40, 52, 64 and 76.
- Mean change in body weight from baseline to Weeks 4, 16, 28, 40, 52, 64 and 76.
- Shifts in physical exam (PE) findings from baseline to Weeks 4, 16, 28, 40, 52, 64 and 76.
- Shifts in neurological exam (NE) findings from baseline to Weeks 4, 16, 28, 40, 52, 64 and 76.
- Mean change in ECG parameters from baseline to Weeks 4, 40 and 76.
- Concomitant medications/treatments usage
- Shifts in the C-SSRS from baseline to Weeks 4, 16, 28, 40, 52, 64 and 76.

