8.8. Pooling With Other Studies

Data from Protocol PTI-125-06 will be pooled with data from Protocol PTI-125-07. These pooled analyses will include data from weeks 0-52 from Protocol PTI-125-06 to match the duration of Protocol PTI-125-07. Objectives and estimands for the pooled data will mirror those in Protocol

Version 1.0 | 28-Feb-2025 Page 30 of 56

PTI-125-07. Analyses will also be similar but will include an additional categorical fixed effect of study. These pooled data will be analyzed using the co-primary and multiplicity adjusted secondary endpoints and by the subgroups defined by baseline composite severity / baseline P-tau categories.

Additional analyses may be applied to the pooled data based on the findings of the PTI-125-06 study.

9. Safety and Tolerability Analysis

All safety analyses will be performed on the safety analysis set.

Safety measures including AEs, clinical laboratory values, physical examination findings, neurologic examination findings, vital signs, ECGs, and concomitant medication usage will be summarized descriptively. No inferential statistical tests will be performed, unless otherwise specified. For quantitative variables, descriptive statistics including number of observations, mean, median, standard deviation, minimum, and maximum will be presented for observed and change from baseline values at each study visit. Qualitative variables will be summarized using counts and percentages.

For all safety and tolerability analyses, participants will be analyzed by the actual treatment and dose received and, if applicable, overall.

All safety and tolerability data will be presented in participant listings.

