9.1.3. Serious Adverse Events (SAEs)

A Serious Adverse Event (SAE) includes (but is not limited to) an experience occurring at any dose that results in any of the following outcomes:

- Death,
- Life-threatening,
- In-patient hospitalization,
- A persistent or significant disability/incapacity,
- A congenital anomaly/birth defect, and
- Other medically important event

The number and proportion of participants who experience the event according to MedDRA system organ class (SOC) and preferred term (PT) will be presented by treatment group. TEAEs

Version 1.0 | 28-Feb-2025 Page 32 of 56

will be further summarized, individually, by maximum severity and relationship to study drug. Adverse events related to study drug, AEs leading to withdrawal, SAEs, and deaths will be similarly summarized.

An overall summary of TEAEs will be provided by treatment. This summary will present number and percentage of participants with TEAEs per the following classifications:

- Participants with any TEAEs
- Participants with Treatment-Emergent Drug-Related AEs
- Participants with Treatment-Emergent AEs by Maximum Severity as Mild, Moderate, and Severe.
- Participants with TEAE leading to discontinuation from study
- Participants with Treatment-Emergent SAEs
- Participants with Treatment-Emergent SAEs leading to discontinuation from study
- Participants with Treatment-Emergent SAEs resulting in death

The following summary tables for TEAEs will be presented:

[figure not shown]
- Number and percent of participants reporting treatment-emergent AEs, grouped by MedDRA system organ class and preferred term
- Number and percent of participants reporting treatment-emergent drug-related AEs, grouped by MedDRA system organ class, and preferred term
- Number and percent of participants reporting treatment-emergent AEs, grouped by MedDRA system organ class, preferred term, and maximum severity
- Number and percent of participants reporting treatment-emergent SAEs will be tabulated by system organ class and preferred term and presented by treatment.
- Number and percent of participants reporting treatment-emergent AEs leading to study discontinuation, grouped by MedDRA system organ class and preferred term

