The observed values and changes from baseline of all quantitative safety laboratory results for clinical chemistry, hematology, and urinalysis (only for pH and Specific Gravity results) will be summarized using descriptive statistics showing the number of observations (n), mean (SD), median, minimum, and maximum value. A separate summary table with the number and percentage of participants for each categorical urinalysis parameter (glucose, protein, occult blood, ketone, nitrite, and leukocyte esterase) will be provided.

Version 1.0 | 28-Feb-2025 Page 34 of 56

Baseline values for all clinical chemistry, hematology, and urinalysis parameters will be categorized as being below the normal range (Low), within the normal range (Normal), and above the normal range (High). Shift from baseline tables will present the number and percentage of participants who have observations that are Normal, Low, or High when such range characterizations are available. Shift tables will be presented for values shifting from Baseline (Study Day 1) to the Week 76/ET/ED.

Listings of all observed chemistry, hematology, and urinalysis laboratory data will be provided. Laboratory results outside the normal range will be flagged. The abnormal values will be flagged with 'L' (low) for values below the lower limit of the laboratory's normal range or 'H' (high) for values above the upper limit of the laboratory's normal range. Abnormal values will be graded as not clinically significant (NCS) or clinically significant (CS).

Abnormal results from the microscopic examination will be listed. All other laboratory assessments will only be listed.

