14.3.5 Laboratory Data Summary Tables		

Version 1.0 | 28-Feb-2025 Page 46 of 56

[figure not shown]
[figure not shown]

Table Number	Population	Table Title/Summary
14.3.5.1.1	Safety	Summary of Laboratory Results - Serum Chemistry
14.3.5.1.2	Safety	Summary of Shift from Baseline in Serum Chemistry Results
14.3.5.2.1	Safety	Summary of Laboratory Results-Hematology
14.3.5.2.2	Safety	Summary of Shift from Baseline in Hematology Results
14.3.5.3.1	Safety	Summary of Laboratory Results -Urinalysis
14.3.5.3.2	Safety	Summary of Categorical Urinalysis Results
14.3.5.4	Safety	Summary of Stopping Criteria by Treatment
14.3.6 Other Safe	ety Data Summary Ta	ables
14.3.6.1	Safety	Summary of Vital Signs Results
14.3.6.2	Safety	Summary of Weights and BMI
14.3.7.1	Safety	Summary of Concomitant Medications
14.3.7.2	Safety	Summary of Concomitant Medications-Cognitive Enhancers Taken Prior to First Dose of Study Drug
14.3.7.3	Safety	Summary of Concomitant Medications-Cognitive Enhancers Taken Post First Dose of Study Drug
14.3.8.1	Safety	Summary of Electrocardiogram Quantitative Results
14.3.8.2	Safety	Summary of Electrocardiogram Interpretation Results
14.3.8.3	Safety	Summary of Observed Categorical ECGs
14.3.8.4	Safety	Summary of Change from Baseline Categorical ECGs
14.3.9.1	Safety	Summary of Physical Examination (Brief) Results
14.3.9.2	Safety	Summary of Neurological Examination (Brief) Results
14.3.10.1	Safety	Summary of Columbia-Suicide Severity Rating Scale (C-SSRS) Suicidal Ideation and Suicidal Behavior Experienced at Any Time Post-Treatment
14.3.10.2	Safety	Summary of Columbia-Suicide Severity Rating Scale (C-SSRS) Suicidal Ideation and Suicidal Behavior by Study Visit
14.3.10.3	Safety	Shift of Columbia-Suicide Severity Rating Scale (C-SSRS) Suicidal Ideation and Suicidal Behavior from Pre-Treatment to Post-Treatment
14.3.10.4	Safety	Shift of Columbia-Suicide Severity Rating Scale (C-SSRS) Suicidal Ideation Scores from Baseline to Treatment Period
14.3.11.1	MRI Sub-study	Summary of MRI Findings

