L16.2.xx.xx	Listing of Volumetric MRI Biomarkers by Visit and Treatment
16.2.7 Adverse Event Li	stings
16.2.7.1	Treatment Emergent Adverse Events
16.2.7.2.	Select Treatment Emergent Adverse Events Used for Renal Function
16.2.8 Laboratory Value	es (by Subject)
16.2.8.1.1	Laboratory Results: Serum Chemistry
16.2.8.1.2	Laboratory Results: Hematology
16.2.8.1.3	Laboratory Results: Urinalysis
16.2.8.1.4	Screening Laboratory Assessments
16.2.8.2	Urine Drug Screen
16.2.8.3	Genotyping Sample Collection
16.2.8.4	Pharmacokinetic Results
16.2.8.5	Subjects Who Met Stopping Criteria
16.2.8.6	Creatinine, eGFR, and Renal Function
16.2.9 Other Clinical Ob	oservations and Measurements (by Subject)
16.2.9.1.1.1	Physical Examination (Complete)
16.2.9.1.1.2	Physical Examination (Brief)
16.2.9.1.2.1	Neurologic Examination (Complete)
16.2.9.1.2.2	Neurologic Examination (Brief)
16.2.9.2.1	Vital Signs
16.2.9.3.1	Prior and Concomitant Medications
16.2.9.3.2	Concomitant Medications – Cognitive Enhancers
16.2.9.4.1	12-Lead Electrocardiogram (ECG) Quantitative Results
16.2.9.4.2	12-Lead Electrocardiogram (ECG) Categorical Results
16.2.9.5	Columbia-Suicide Severity Rating Scale (C-SSRS)
16.2.9.6.1	COVID-19 Impact

Version 1.0 | 28-Feb-2025 Page 49 of 56

Data Listing Number	Table Title/Summary	
16.2.9.6.2	COVID-19 Study Drug Impact	
16.2.9.7	Follow-up Phone Calls	

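### The by-arm stopping-criteria table counts ALP crossings at 2.5x or 3x ULN only if judged hepatic and drug-related, and no other planned SAP output counts them

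*SAP*

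**What the plan says.** SAP 9.2.1 restates the stopping criteria of protocol 7.1.11. The three ALT/AST criteria are stated on laboratory values, or on values with bilirubin or symptoms. The three ALP criteria (above 3x ULN; above 2.5x with total bilirubin above 2x; above 2.5x with listed symptoms) come under one heading: "ALP elevations, if deemed of liver origin and drug-related as follows". Two C-SSRS criteria and one weight/BMI criterion follow.

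The section then says that individual results will be listed and "summarized by presenting the number and percentage of participants who meet at least one post-dose stopping criteria". In SAP section 13 this becomes Table 14.3.5.4, "Summary of Stopping Criteria by Treatment", and Listing 16.2.8.5, "Subjects Who Met Stopping Criteria".

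In protocol 7.1.11 the same wording guides the investigator, in consultation with the medical monitor, on whether to consider stopping drug in an individual subject.

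**The concern.** A judgement of causality belongs in a decision about one patient. As a counting rule for comparing arms, it removes cases before the comparison that would help to judge causality. Here the filter applies only to ALP, and the by-arm table then merges the liver criteria with suicidality and weight in a single figure.

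At stake is the ability to see a cholestatic signal in the one table that applies the liver thresholds. Protocol 2.2 gives a reason to look. In the 6-month rat study, animals at 500 and 1000 mg/kg/day had liver changes with bile pigment consistent with cholestasis, and raised ALP and bilirubin. The NOAEL in that study, 50 mg/kg/day, gave a 1.6-fold AUC margin over 100 mg b.i.d.

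**Working it through.** The plan states no figure on this point to reproduce. The check has three parts.

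**1. Which criteria carry the attribution condition (SAP 9.2.1)**

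| Group | Criteria | Conditional on attribution |
|---|---|---|
| ALT/AST | 3 | 0 |
| ALP | 3 | 3 |
| C-SSRS | 2 | 0 |
| Weight/BMI | 1 | 0 |

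Total: 3 + 3 + 2 + 1 = 9 conditions merged into one figure, of which 2 + 1 = 3 are not hepatic.

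**2. Whether another SAP output supplies the missing count**

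- Table 14.3.5.4: conditional, as above.
- Listing 16.2.8.5: by its title, limited to those who met the criteria. An unattributed ALP case is absent unless another criterion is met.
- Chemistry summary (SAP 9.2, Table 14.3.5.1.1): n, mean, SD, median, minimum and maximum by visit. A maximum is one value, not a count of participants, and is not paired with that participant's bilirubin.
- Chemistry shift table (SAP 9.2, Table 14.3.5.1.2): by arm and free of attribution, but only Low, Normal or High. SAP 9.2 says "Shift tables will be presented for values shifting from Baseline (Study Day 1) to the Week 76/ET/ED", while SAP 3.2.1 lists "Shifts in the normality of clinical laboratory values from baseline to Weeks 4, 16, 28, 40, 52, 64 and 76". On either reading, 1.1x and 5x ULN fall in the same cell.
- Chemistry listing (16.2.8.1.1): every value with a high or low flag, but no count.
- Adverse event tables (SAP 9.1.3): "Number and percent of participants reporting treatment-emergent AEs, grouped by MedDRA system organ class and preferred term". These cover all causalities, but they count MedDRA terms rather than multiples of ULN. Protocol 10.1 gives new clinically significant laboratory abnormalities as examples of adverse events, so judgement enters here too.
- Remaining safety outputs concern renal function, ECG, vital signs, examinations, C-SSRS, MRI and medications.
- DSMB outputs are outside this SAP (section 1).

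None of these counts ALP above 2.5x or 3x ULN, alone or with bilirubin, regardless of attribution.

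By contrast, SAP 9.4 counts participants by QT, QTcB and QTcF thresholds with no attribution condition, although protocol 2.2 reports no adverse effect in the hERG test or the dog cardiovascular study.

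**3. How much could be lost**

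Neither the crossing rate nor the share attributed is in the documents. For illustration, assume k = 5 participants in an arm cross an ALP criterion on measured values and recorded symptoms, and each is attributed independently with probability a. Then:

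- expected count through the ALP criteria = k × a
- chance that these criteria count nobody = (1 − a)^k

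| a | Expected count | Chance of none |
|---|---|---|
| 0.10 | 5 × 0.10 = 0.5 | 0.90^5 = 0.590 |
| 0.25 | 5 × 0.25 = 1.25 | 0.75^5 = 0.237 |
| 0.50 | 5 × 0.50 = 2.5 | 0.50^5 = 0.031 |

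If a is the same in every arm, the expected difference between arms also shrinks by the factor a. That is thinning of the signal, not bias in its direction.

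**The case against.** The strongest reply is that the table does what its title says. It reports how many participants met the protocol's stopping criteria, and SAP 9.2.1 reproduces those criteria faithfully. ALP also rises from bone, which is a reason for a qualifier on ALP alone. This stands in part: the attributed count is a legitimate row and should stay. It does not explain why no unattributed count exists beside it. Screening excluded ALP at or above 1.5x ULN (exclusion criterion 23), so a later value above 2.5x generally reflects a rise on study. GGT is measured at every visit, which helps a reader judge liver origin.

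Second, much of the information is available elsewhere. A large ALP rise would show in the visit maxima and the chemistry listing, and a cholestatic case with raised transaminases enters through the ALT/AST criteria. That is true, but none of these is a by-arm count at the thresholds.

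Third, the table shell is not in the documents and the SAP names no field holding the attribution, so the actual programming cannot be seen. The sentence on listing individual results might also be read more broadly than the listing's title. This is fair, and the point rests on the text as written. If the intention is to count on measured values, the text still needs changing.

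Fourth, the toxicology is mixed. The cholestatic findings came at 10 and 20 times the NOAEL dose to which the 1.6-fold margin belongs. For the second 6-month rat study, protocol 2.2 reports vacuolation and hypertrophy at 125 and 250 mg/kg but no ALP rise. The 9-month dog study had no pathology findings, and its NOAEL gave margins of 38- and 19-fold. This stands, and it limits the weight of the concern.

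Last, the symptom criterion needs a rule for association in time. The unconditional ALT/AST symptom criterion needs the same rule, so one rule can serve both.

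**Conclusion.** The concern holds. As written, an ALP crossing at 2.5x or 3x ULN counts towards Table 14.3.5.4 only after attribution to liver and drug, and no planned SAP output gives the unattributed count. The conclusion about the SAP text is firm; the number of participants affected is unknown, and the illustration rests wholly on assumed values of k and a and on independence.

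The consequence is modest. Safety analyses are descriptive (SAP section 9: "No inferential statistical tests will be performed, unless otherwise specified"), treatment is blinded, no bias between arms is shown, and no efficacy result is touched. This is a worthwhile, cheap improvement rather than a defect that threatens the trial's conclusions.

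**What to change.** In SAP 9.2.1 and Table 14.3.5.4:

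- Tabulate each stopping criterion separately by arm, and keep the row for meeting any of them.
- Count the three ALP criteria at any post-dose visit on measured values and recorded symptoms, regardless of attribution.
- Show the subset judged hepatic and drug-related as a second row, and name the field that records that judgement.
- Apply one timing rule to the symptom criteria for both ALP and ALT/AST.
- In Listing 16.2.8.5, include the unattributed ALP crossings with a flag.

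The cost is SAP wording and a few extra table rows and listing lines from data already collected. The unfiltered ALP rows will include some elevations of bone origin; the second row and the GGT values help a reader separate them.

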All statistical comparisons will be based on LS means from the relevant contrasts in the mixed model for repeated measurements (MMRM) or analysis of covariance (ANCOVA).

The data from nominal/scheduled protocol clinic visits will be included in visit-based summary tables. Unscheduled assessments, if they occur, and the ET visit data will be mapped to scheduled assessments according to the visit windows defined in section 6.1.5 for all safety and efficacy analyses. See Section 6.1.4 and 6.1.5 of this SAP for more details.

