6.1.5. Analysis Visit Windows

All scheduled visits and associated variables for the treatment phase will be analyzed based on the study week to which they are assigned.

For the safety summaries and analyses, scheduled analysis visits will be windowed to the nearest scheduled visit and the unscheduled visits/assessments and early termination visits will be mapped to a scheduled visit using the following visit windows (Table 2.1 and Table 2.2). Visit windows will be assigned by splitting the periods between visits at the mid-point between the visits.

If both scheduled and unscheduled visits fall within the same visit window, scheduled visit will be used over unscheduled visits. If both scheduled and early termination visits fall within the same visit window, the data from the early termination visit will supersede.

If more than one unscheduled visit falls within the same visit window, the one closest to the target date will be used in the analysis. If equidistant, the earliest visit will be used.

If the analysis visit (for Unscheduled or ET assessments) falls on a visit window in which that specific assessment is not scheduled, then that assessment will not be used for analysis.

Table 2.1: Visit Windows for Safety (Except for ECG) Analysis

Scheduled Visit	Scheduled Visit Day	Window for Assignment of
	(Target Day)	Analysis Visit (Study Days ¹)
Week 4	Day 29	Day 2 – Day 71
Week 16	Day 113	Day 72 – Day 155
Week 28	Day 197	Day 156 – Day 239
Week 40	Day 281	Day 240 – Day 323
Week 52	Day 365	Day 324 – Day 407
Week 64	Day 449	Day 408 – Day 491
Week 76	Day 533	Day 492 – Day 575

¹Study Day relative to the date of first dose of study drug.

Table 2.2: Visit Windows for Safety (ECG only) Analysis

Scheduled Visit	Scheduled Visit Day	Window for Assignment of
	(Target Day)	Analysis Visit (Study Days ¹)
Week 4	Day 29	Day 2 – Day 155
Week 40	Day 281	Day 156 – Day 407
Week 76	Day 533	Day 408 – Day 659

¹Study Day relative to the date of first dose of study drug.

For the efficacy summaries and analyses, scheduled analysis visits are visits upon scheduled time points as specified in the Schedule of Time and Events. Scheduled analysis visits will be windowed

Version 1.0 | 28-Feb-2025 Page 21 of 56

to the nearest scheduled visit. Assessments that fall within the same window will be averaged. There will be one valid value of assessment kept for each scheduled analysis visit in summary / analysis statistics.

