For partial end dates: (a) if only the day is missing, then the day is assigned the last day of the month; (b) if both day and month are missing, they are assigned the last day of the year (31DEC).

For analysis purposes, repeat laboratory results will not be used unless the original value is indicated as missing or invalid. In such cases, the first non-missing repeat value will be used for data analysis. The international system of units (SI) will be used in reporting all laboratory values.

Participants will be analyzed by the treatment received for all safety and tolerability assessments.

Participants are stratified through the IRT system based upon MMSE score entered. Once an MMSE score is entered, that participant is randomized to either high MMSE (21-27) or low MMSE (16-20) strata. At study start, it was decided to stratify participants in this manner so there would be a balance in the number of participants on placebo vs active drug (and within treatment arms) within each stratum. The stratification of the participants does not impact their probability of being

Version 1.0 | 28-Feb-2025 Page 23 of 56

assigned to different treatment arms. Once randomized through IRT, the MMSE score and the stratification assigned cannot be changed.

For instances where the MMSE score was incorrectly entered into IRT, the MMSE score given by the vendor will be used to calculate the strata for safety and efficacy analyses if there are any subgroup analyses.

All collected data will be presented in listings. Data not subject to analysis according to this plan will not appear in any tables or graphs but will be included only in the data listings.

A treatment related AE is any AE with a relationship to the study drug of "Possibly Related" or "Probably Related" or "Reasonable Possibility".

If partial dates occur, the convention for replacing missing dates for the purpose of statistical analysis is as follows: if just day is missing then the day assigned is the first day of the month or the date of first dose (if in the same month), whichever is later; if just month is missing then the month assigned is the month of the first dose, unless that results in a date before the first dose in which case the month after the first dose is used; and if both month and day are missing then the month assigned is the month of the first dose and the day assigned is either the first day of the month or the first dose date, whichever is later.

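### Table 14.3.5.4 has no stated data source, the SAP's default record rules can drop a peak liver value, and its single merged count can obscure a liver imbalance between arms

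*SAP*

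**What the plan says.** SAP 9.2.1 describes three families of criteria for stopping study drug. The liver family is for a participant who "meets one or more of the following liver chemistry threshold stopping criteria" and covers ALT/AST and ALP limbs. The suicidality family begins "Study drug should be discontinued if a participant: (1) positively affirms suicidal ideation" and adds suicidal or self-injurious behaviour. The third is weight loss leading to a low BMI. For reporting, "Individual results of stopping criteria will be listed", and they are also "summarized by presenting the number and percentage of participants who meet at least one post-dose stopping criteria". The outputs are Table 14.3.5.4, by treatment, and Listing 16.2.8.5. Section 9.2.1 names no record source.

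Three general rules bear on which records are used:

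- SAP 4.2 maps unscheduled and ET data to scheduled visits through the 6.1.5 windows "for all safety and efficacy analyses".
- SAP 6.1.5 resolves competing records. Between a scheduled and an unscheduled record, "scheduled visit will be used over unscheduled visits". For ET, "If both scheduled and early termination visits fall within the same visit window, the data from the early termination visit will supersede". Among several unscheduled records, the one nearest the target day is kept.
- SAP 6.1.8 says that "repeat laboratory results will not be used unless the original value is indicated as missing or invalid".

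Section 9.2.1 states no exception and no worst-value rule.

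**The concern.** A stopping-criteria count asks whether a participant ever crossed a threshold. Rules that choose one representative value per visit answer a different question, because they select on visit type and timing and ignore the size of the value. The participants most exposed are those whose raised enzymes were found and acted on. Protocol 9 requires clinical laboratory tests at discharge from everyone who leaves the study early, and its 30-day exemption covers only the rating scales. A withdrawal prompted by a liver result therefore tends to produce a later ET sample, taken after drug has stopped.

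The merged count is a separate matter and does not depend on how windowing is read. C-SSRS has its own tables (SAP 9.8) and weight and BMI have a summary (SAP 9.3), but no other planned table applies multiples of ULN. A by-arm view of threshold liver events therefore rests on a figure that also contains unrelated events. Liver is a reasonable organ to watch. Protocol 2.2 reports adverse liver findings in the 6-month rat study, with a 1.6-fold AUC margin at the NOAEL over 100 mg b.i.d. The same section reports no pathology findings in the 9-month dog study and a 19-fold AUC margin at its NOAEL.

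**Working it through.** **1. Rebuild the windows.** The inputs are the target days in SAP Table 2.1: 29, 113, 197, 281, 365, 449 and 533. The upper limit of each window is the midpoint to the next target: (29 + 113)/2 = 71, (113 + 197)/2 = 155, then 239, 323, 407 and 491. The last is 533 + 42 = 575. This reproduces Table 2.1 exactly: Day 2–71 (70 days), then six windows of 84 days.

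**2. How late an ET visit can be and still replace a scheduled value.** For Week 40, 323 − 281 = 42. An ET visit 1 to 42 days after an on-target scheduled visit shares its window and takes its place. Day 281 and Day 300 share the Day 240–323 window, so 5x ULN on Day 281 followed by 2.5x ULN at ET on Day 300 is analysed as 2.5x.

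**3. Apply the priority rules to constructed records.** ALT is in multiples of ULN. The limb tested is ALT or AST at or above 4x ULN.

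| Case | Records | Value kept | Met, windowed | Met, all values |
|---|---|---|---|---|
| A | scheduled Day 113: 2.5; unscheduled Day 120: 5.0; ET Day 134: 1.8 | 1.8 | no | yes |
| B | scheduled Day 113: 5.0; ET Day 134: 1.8 | 1.8 | no | yes |
| C | unscheduled Day 100: 5.0 and Day 112: 2.0; no scheduled visit | 2.0 | no | yes |
| D | single unscheduled Day 120: 5.0, alone in its window | 5.0 | yes | yes |
| E | scheduled Day 113: 5.0; next visit Day 197 | 5.0 | yes | yes |

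The rules count two of the five, whereas using all values counts all five. The cases were built to show the mechanism and do not estimate how often it occurs.

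**4. Direction of the repeat rule.** Section 6.1.8 keeps the original result and sets the repeat aside. If a high value is repeated and comes back lower, the peak is preserved. A case is lost only when the repeat is the higher value.

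**5. Dilution by merging.** Let p be the liver rate and b the rate of meeting a non-liver criterion, assumed equal in both arms and independent of p. The merged rate is 1 − (1 − p)(1 − b). With b = 5%, p = 0.5% gives 1 − 0.995 × 0.95 = 0.0548 and p = 3% gives 1 − 0.97 × 0.95 = 0.0785, a ratio of 1.43. The documents give no rates, so all of these are assumptions, shown over a range:

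| Liver rates | Liver-only ratio | Merged, b = 2% | Merged, b = 5% | Merged, b = 10% |
|---|---|---|---|---|
| 0.5% vs 2% | 4.0 | 1.59 | 1.26 | 1.13 |
| 0.5% vs 3% | 6.0 | 1.98 | 1.43 | 1.22 |
| 0.5% vs 4% | 8.0 | 2.38 | 1.61 | 1.30 |

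At the planned 361 per arm, the middle row with b = 5% turns about 1.8 against 10.8 liver cases (361 × 0.005 and 361 × 0.03) into about 19.8 against 28.3 merged cases (361 × 0.05475 and 361 × 0.0785).

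**6. Whether other outputs supply the count.** The laboratory shift tables in SAP 9.2 run from baseline to Week 76/ET/ED and use Low, Normal and High, so they give no multiples of ULN and no worst value. By-visit maxima would come from windowed data. Listing 16.2.8.5 would miss the same participants if it uses the same derived flag. The listings of all observed chemistry do keep every value.

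**The case against.** The strongest reply is that section 9.2.1 can be read as already asking for any post-dose value. The count is per participant, the table is by treatment with no visit dimension, and the windowing paragraph in SAP 4.2 opens with visit-based tables. A reader might infer that the table is definitely built from one windowed value per visit, but the SAP does not say so, and some limbs also need symptoms or a judgement about cause. What stands against the reply is that 4.2 ends by extending the windows to all safety analyses, and 9.2.1 makes no exception. SAP 9.8 does state an any-time rule for C-SSRS, so the SAP says so where it wants one.

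A reader might also infer that anyone who improves by an ET visit in the same window is always missed. That does not follow. The ET value may still be above threshold, another window may hold a qualifying value, or another criterion may be met. Nor does stopping drug always bring an early ET visit: the protocol separates stopping drug from leaving the study, allows restart (7.1.10), and makes the liver limbs something to consider (7.1.11).

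A third tempting inference is that liver toxicity is hidden. It is not. All observed chemistry is listed and flagged, adverse events are tabulated by preferred term (including those leading to study discontinuation), and the C-SSRS and weight components have their own tables. Per-criterion rows are not ruled out by the table title either. These points limit the consequence. They do not supply a by-arm count of participants crossing a liver threshold.

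**Conclusion.** The point holds as a gap in specification with a real consequence under the default rules. A participant who met a liver threshold can be counted as not meeting it when a lower ET or scheduled value shares the window, or when an unscheduled value nearer the target day is lower, provided no other retained value or criterion qualifies. Separately, the only specified summary merges three unrelated families, so a liver difference between arms can be obscured in the summary tables while remaining recoverable from raw listings and adverse-event tables.

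The frequency cannot be estimated from the documents. The windows show that the opportunity is wide (up to 42 days after an on-target visit). The dilution figures rest on assumed rates, an equal non-liver background in both arms, and independence. The severity is should-fix: safety analysis here is descriptive, and the estimands, error control and primary conclusions are unaffected.

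**What to change.** In SAP 9.2.1, and in the specifications for Table 14.3.5.4 and Listing 16.2.8.5:

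- State that each flag is derived from every post-dose result (scheduled, unscheduled, repeat and ET), outside the 6.1.5 windows and the 6.1.8 repeat rule.
- Report one row per criterion by treatment arm: each ALT/AST limb, each ALP limb, C-SSRS, and weight/BMI. Keep the row for any criterion.
- For limbs that need more than a laboratory value, name the records that supply the symptom or attribution element.

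The clinical thresholds are unchanged. The cost is SAP wording and some extra table programming. The laboratory data are already collected and listed.
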